3.1 Study area, settings, and population

The study is anchored in the settings of CHNs in the municipalities of the Child Health Database, CHD, (159) and conducted among the municipalities who have implemented the basic PUF-program in 2018-2019 (154) and 2020. The study municipalities are overall representative of the municipalities in the Child Health Database and the Danish population regarding key background characteristics (160).

Anticipated number of participants

By 1st of October 2020, a total of sixteen municipalities consented to participation, and we expect all of them to complete participation in the study. The 16 participating municipalities have around 8280 births per year in total (161). Based on the primary planned recruitment period of 16 months (1.3.2021-30.6.2022) an estimated ~10,350 infants will reach 9-10 months during the data collection period. Based on data from the Child Health Database (162), we expect around 88% of the children (~9,100) born in the study municipalities to receive home visits at age 9-10 months and be assessed by the PUF-measure as well. Based on previous research (26, 147, 150, 152, 154), we

INFANT HEALTH

estimate that about 16% of children assessed with the PUF method have three or more (≥ 3) problems indicating major developmental or regulatory problems. Children will be excluded from study if they have severe mental or physical disabilities or if their parents have major problems in speaking or understanding Danish or English. It is expected that a total of 5% of the population meet the exclusion criteria, which leaves us with $\sim 8,650$ children estimated to be eligible for the PUF assessment and around $\sim 1,380$ children eligible for participation in the study.

Status October 2022:

The outbreak of the COVID pandemic in the beginning of March 2020 has had an immense influence on the study-flow and the recruitment rate in the participating municipalities, which at times has ranged from 70% in some municipalities to zero in others. Consequently, we have had to extend the overall study period including the recruitment period, and strong efforts have been made to intensify the recruitment in the individual municipalities. The PUF-program education to correctly identify the vulnerable children, has thus been boosted, delivering regular brush-up courses by special educated project CHNs. A total of seven of these project CHNs have been allocated to the Infant Health Study, to further intensify the identification of children meeting the criteria of inclusion, and specifically, to intensify the support to the CHNs in municipalities having low rates of recruitment.

During 2021-2022, the recruitment aims have been adjusted. Firstly, the launch of the recruitment period has been postponed to August 16, 2021, and next, the period of recruitment has been extended to October 31, 2023. Based on the frequency of children identified with three or more vulnerabilities so far, we have adjusted the overall expected identification rate from 16 pct. to 10 pct. of the screened children, with some municipalities recruiting up to 70 % of what we expect, while others only recruit 30% or even less. Still, throughout the recruitment period we have realized a relatively high rate of participation among eligible children invited for participation.

Per October 2022, the recruitment aims are adjusted to comprise around 780 children at baseline, and around 460 children available for the follow-up at 24 months (see Figure 1).

For further sample size justification please see section 4.2.

Supplementary information October 2024

June 2024-october the data collection in project was forced to pause caused by discrepancies in the ethical evaluations completed by the Research Ethics Committee REC University of Southern

INFANT HEALTH

Denmark in 2020 and 2022, and the local Committees on Health Research Ethics in the Capital Region of Denmark June 2024. After approval of the project continuation in the remaining period of data collection from the local Committees on Health Research Ethics, research activities were re-up taken October 2024.

Per October 2024, the around 471 children available for the follow-up. At that time, participation of controls and cases at ages the 18 months assessments were 90% and 83%.

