result in a larger sample size and less frustration about recruitment among the CHNs who find it very hard to deliver standard care to families, when they have introduced an intervention, they believe is superior. Thus, we believe that the stepped wedge design is associated with the least dropout.

On a practical level, the 16 participating municipalities will be randomly distributed into three clusters (6+5+5), and clusters will be randomized to initiate intervention at three different time points, according to the stepped-wedge design (see Figure 1, flow diagram revised October 2022) (Detailed overview of the design, see Appendix 1).

Figure 1. CONSORT diagram

INFANT HEALTH

Randomization and screening (PUF) at child-age 9-10 months

According to the randomization of municipalities, all children assessed to have ≥ 3 problems will function as controls and receive care as usual from Step 0 until the municipalities initiate the intervention in Step 1- 3, respectively.

Recruitment of municipalities, children, and parents

INFANT HEALTH

[figure not shown]
All municipalities that have implemented the basic PUF-program are invited, and the leading CHNs from the becoming study municipalities are invited to join the study planning group as key stakeholders.

In the participating municipalities, the parents of children becoming 9-10 months in the study period are informed about the project by the CHNs, and via written folders and information on the study home page (<https://www.sdu.dk/da/sif>). At the scheduled home visit at child ages 9-10 months, the CHNs complete PUF-assessment and offer the parents feedback in accordance with the basic PUF-program and the existing routines. All parents of children who have been assessed to have three or more problems are offered extended service, in the control phase of the study this is delivered in accordance with the existing routines of the CHNs in the particular municipalities (care as usual), whereas the CHNs offer the VIPP-PUF intervention to parents in the intervention phase. The CHN informs all parents of infants full-filling the study criteria of inclusion about the details in the Infant Health project, and if parents are interested, they are invited for participation by e-post. Parents make their final agreement for participation by answering the web-based questionnaires at the study website.

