Based on estimates of the number of vulnerable infants fulfilling the criteria of inclusion and the need of minimum two CHNs educated in the PUF-VIPP method per municipality, a total of 49 CHNs have been educated in the VIPP-PUF method since June 2021. The VIPP-PUF education consists of a four-days course including teaching in the theoretical basis of the VIPP, building on attachment theory and theories of mentalization and social learning, as well as the developmental approach of the PUF-program integrating case-based learning and practical exercises. The initial VIPP-PUF course is followed by training in using the VIPP-PUF intervention to parents of a child aged 9 to 12 months, notably a child without problems and from a non-vulnerable family. During this training the CHNs receive individual supervision in groups by a certified supervisor from the VIPP- Institute, Leiden, the Netherlands, delivered before each of the five home visits in the training period. Next the CHNs receive a one-day booster course in the VIPP-PUF method around one week ahead of intervention start in their municipality. During her first VIPP-PUF intervention to a vulnerable child, the CHN receives two sessions of individual supervision by a certified supervisor, alternating with peer-supervision in groups led by experienced VIPP-PUF CHNs. The evaluation of the VIPP-PUF intervention includes an evaluation of the needs of educating specific Danish VIPP-PUF supervisors in collaboration with the VIPP Institute, this to ensure the sustainability of the VIPP-PUF training and supervision during the project period and beyond.

Development of intervention components

The specific tools and activities of the intervention will be developed in a participatory planning group and in dialogue with the Project Steering Group.

Educational experts, graphic- and web-designers, videographers and writers will be consulted to develop the web-platform and extended scripts, plans, visual and written outlines (booklets, leaflets/handouts/newsletters) and video demos (visual presentation of information, skills training, and case situations).

Focus discussions involve CHNs from the study area and parents, recruited by local CHNs (WP4).

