4.2 Statistical analyses

Statistical analyses will be carried out according to the intention to treat principle, where the participants are analyzed according to their CAU/intervention recruitment group. For continuous outcomes (including the primary outcome measured as the SDQ total difficulties score), linear mixed models will be fitted to compare the control group receiving care as usual (CAU) and the VIPP-PUF intervention group. For binary outcomes (e.g., border line/abnormal versus normal SDQ score), logistic mixed-effects regression models will be fitted to compare the control and intervention groups. All models include municipality-specific random effects, allowing for the correlation between outcomes of children from the same municipality. Likewise, cluster-specific random effects will be included.

Differences in weight-for-length between intervention and control groups will be evaluated using analysis of covariance (ANCOVA). Associations between weight-for-length z-score and selected risk factors based on their associations with infant behavior and preschool obesity in the published literature will be explored using linear regression. To assess differences in parental feeding practice and infant eating behavior between intervention and control groups, mean scores on the feeding and eating questionnaires subscales are calculated and analyzed using linear mixed models for repeated measurements, including participant-specific random effects. Further, exploratory analyses regarding feeding practices, eating behavior, and weight development will be carried out.

Other prognostic factors identified from the literature *á priori* will be included in analyses. Examples include parents’ education, employment status, household income, ethnicity, parental age, parental mental health problems and marital status (all obtained from national registers) (160); at the child level, sex, birth parameters, weight-for-length z-scores from birth to age 9 months, regulatory problems from ages 2-9 months, and ASQ:SE2 score at 9-10 months; and at the

INFANT HEALTH

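### Entry severity could differ by phase: children enter on a PUF threshold scored with the phase known, identification was intensified during the project, and the primary model names neither the PUF count nor a period term

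*Protocol*

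**What the plan says.** **Entry.** Protocol 3.2 states: "At the scheduled home visit at child ages 9-10 months, the CHNs complete PUF-assessment". Three or more problems make a child eligible. Before crossover, "all children assessed to have ≥ 3 problems will function as controls and receive care as usual from Step 0". After crossover the offer changes: "whereas the CHNs offer the VIPP-PUF intervention to parents in the intervention phase". Section 3.5 adds: "Next the CHNs receive a one-day booster course in the VIPP-PUF method around one week ahead of intervention start in their municipality". No section describes masked PUF scoring or an independent rater. The design rationale in 3.2 mentions "CHNs who find it very hard to deliver standard care to families, when they have introduced an intervention, they believe is superior".

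**Identification.** The October 2022 status in 3.1 reports: "The PUF-program education to correctly identify the vulnerable children, has thus been boosted, delivering regular brush-up courses by special educated project CHNs". It adds seven project CHNs, with particular support for low-recruiting municipalities. Recruitment is given as 16 August 2021 to 31 October 2023. The expected share of screened children with three or more problems was revised from 16% to 10%. Section 3.2 says that control families come from the early part of the trial and that crossover cannot be reversed.

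**Analysis.** Section 4.2 compares SDQ total scores by recruitment group in a linear mixed model with municipality and cluster random effects. It names no step or calendar-period effect. Its child-level prognostic factors, given as examples, end with "regulatory problems from ages 2-9 months, and ASQ:SE2 score at 9-10 months". Section 3.7 (WP 3a) adds nurses' records from visits up to 6 months and again the baseline ASQ:SE2. Neither list names the 9-10 month PUF count.

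The Combined protocol and SAP has the same text on all these points.

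**The concern.** Randomising municipalities balances the populations from which children are drawn. It does not balance the children who enter, because they are selected after allocation by staff who can be expected to know the phase. Two routes could separate the phases in entry severity. The threshold could be applied differently once a count of three opens a different service. Identification could also change over calendar time, and in this design calendar time is tied to phase.

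If entrants differ in severity, their natural course to 24 months differs too, and part of the SDQ contrast would reflect selection rather than VIPP-PUF. The measure that defines entry is the obvious baseline value to adjust for and to tabulate by phase. Section 4.2 commits to neither.

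**Working it through.** **1. The plan's own figure, for scale.** Inputs from 4.2: difference 2, SD 5.7, alpha 0.05 (taken as two-sided), power 80%, ICC 0.001, three clusters.
- Per arm: 2 × (1.960 + 0.842)² × 5.7² / 2² = 127.5, so 128, or 256 in total.
- The design effect is 1 + (m − 1) × 0.001. The plan does not state m. A total of 306 needs m = (306/256 − 1)/0.001 + 1 ≈ 196. Taking m = 780 × 0.70/3 = 182 gives 302, close to 306.
- Follow-up: 780 × 0.85 × 0.70 = 464, against the stated 460.

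These figures reproduce and this point does not affect them. They supply the 2-point yardstick and the SD.

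**2. Is the phase known at scoring?** This is not stated in so many words. It follows from CHNs offering VIPP-PUF only after crossover (3.2) and from the booster course about a week before local start (3.5).

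**3. Does identification overlap with phase?** The boost is reported in October 2022, inside the August 2021 to October 2023 window. With controls first and no return, any change partway through recruitment tends to fall more on intervention-phase children. The actual overlap cannot be computed, because the text available does not date the boost against the steps.

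**4. How large could an imbalance be?** Assumptions not in the documents: normal latent severity; nurses identify the most severe share p; correlation r between severity and 24-month SDQ of 0.2-0.4; SDQ SD from 4.5 (assumed) to 5.7 (from 4.2); no covariate adjustment; and a complete phase difference in p from 10% to 16%. The documents do not report such a rise. The two values are the revised and the first expected rates.
- Mean severity of the selected share = φ(z_p)/p.
- p = 0.10 gives 1.755 SD and p = 0.16 gives 1.521 SD, a difference of 0.234 SD.
- Low end: 0.234 × 0.2 × 4.5 = 0.21 points. High end: 0.234 × 0.4 × 5.7 = 0.53 points.
- Divided by 2 points: about 10% to 27%.

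Partial overlap between the change and the phases shrinks this in proportion.

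**5. Effect on a null trial.** Take 460 children in two equal groups, with design effect 1 + (460/3 − 1) × 0.001 = 1.152. The SE is 5.7 × √(4 × 1.152/460) = 0.571. With no true effect, two-sided rejection is 5% at zero bias, about 7% at 0.25 points and about 14% at 0.5 points.

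**6. What each model term would remove.**
- If scoring is honest but more children near the threshold are found, the PUF count captures much of the change.
- If the scoring itself shifts with phase, the count shifts too and adjustment is incomplete.
- A period effect absorbs identification changes common to all municipalities. It does not absorb support aimed at particular municipalities, or scoring that changes at crossover.

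Tabulation by municipality and phase is therefore needed alongside the model terms.

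**The case against.** **Incentive.** Section 3.2 offers extended service to families of children with three or more problems in both phases, so a count of three brings extra help throughout. The remark about nurses' belief in the intervention explains the choice of design and does not concern PUF scoring. Section 3.5 reports 49 CHNs trained in VIPP-PUF, with at least two needed per municipality, and nowhere is the scoring nurse said to be the delivering nurse. This stands: the incentive differs in degree only.

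**Cause and direction.** A reader might infer that the courses were added because identification had fallen to 10%, and that intervention-phase children are therefore milder. The documents do not support this. Section 3.1 ties the boost to COVID and low recruitment, and describes its aim as correct identification. Training that recovered missed severe cases would push the bias against VIPP-PUF.

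**Size.** A reader might also turn the 30% and 70% figures in 3.1 into a before-and-after change in identification and reach a larger bias. Those are recruitment shares in different municipalities, not rates before and after crossover, so they are not used here.

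**Existing handling.** The covariate lists are open, ASQ:SE2 at 9-10 months is planned, and regulatory problems at 2-9 months may overlap PUF content. The steering committee (section 7) may raise systematic recruitment bias, and Table 1 in 3.8 compares participants with non-participants. This stands as partial cover. However, no method is given for the committee's check, Table 1 does not plan a comparison by phase, and an open list does not commit the analysis to the PUF count.

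**Conclusion.** The point holds as a risk of imbalance that the plan neither adjusts for adequately nor arranges to detect. It is not a demonstrated bias in favour of VIPP-PUF. Three facts carry it: selection after allocation in an openly phased rollout, intensified identification reported inside the recruitment window, and a primary model that names neither the entry-defining PUF count nor a period term.

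The 0.2-0.5 points (10-27% of the planned effect) is an illustration. It rests on the severity model, the correlation range, a complete 10%-to-16% difference between phases and no adjustment. The planned ASQ:SE2 adjustment would remove some of it, by an amount that cannot be computed from the documents. The true value may be zero or of opposite sign. The change is worth making because it is cheap and because only data by phase can show whether an imbalance arose.

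**What to change.** In 4.2, before outcomes are compared by phase:

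1. Prespecify the 9-10 month PUF problem count and baseline ASQ:SE2 as fixed covariates in the primary SDQ model, with a calendar-period (step) effect.
2. Report by municipality and phase: PUF assessments done, share with three or more problems, mean PUF count, baseline ASQ:SE2, and share of eligible families who joined.
3. State that the PUF count is scored by nurses aware of the phase, so adjustment reduces the bias but may not remove it.

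A sensitivity analysis restricted to four or more problems is optional; that cut can drift as well. Weighting for participation should be added only if PUF data on non-participants are confirmed to be available. Section 3.8 names registers and the Child Health Database for them, not PUF scores.

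**Cost.** Trial conduct does not change. Entry depends on the PUF count, so it should exist for every participant. The period term costs precision. As a rough guide, assume equal enrolment per municipality over Steps 0-3, the 6+5+5 split and negligible clustering. The treated shares are then 0, 6/16, 11/16 and 1. The mean within-step variance of treatment is (0 + 0.234 + 0.215 + 0)/4 = 0.112, against 0.250 overall (0.516 × 0.484). The SE rises by √(0.250/0.112) ≈ 1.5. The sponsor should repeat this with the actual step dates and enrolment.

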3.2 Design

We have chosen the stepped wedge cluster randomized design (163-165) mainly for two reasons. First, it is more feasible to randomize at the municipality level as compared to the level of the individual child or CHN. An RCTs based on randomization of the individual child or nurse would be associated with more logistical demand on the individual municipality or nurse as compared to the stepped wedge design as they would be having both the intervention and the control condition running simultaneously. For practical reasons, all municipalities cannot be trained at the same time but have to be split into three groups, and with the stepped wedge design we utilize this and randomly allocate the 16 participating municipalities to the time at which their health nurses have been trained and start offering the intervention to families. Also, with the SWD spill over is reduced by the randomization of clusters as compared to individual randomization. Second, in the stepped wedge design, interventions are introduced in a stepwise manner to all participating clusters (municipalities in this case) which encourages participation for those who would otherwise have been randomized to the control condition. Initial feedback from our interactions with the municipalities reveals that their motivation is strongly associated with being able to offer the intervention, as many municipalities prioritize early intervention highly. Also, with the stepped wedge design control families are recruited in the early phases of the trial, which enhances the recruiting of a control group with the level of usual care offered at the beginning of the trial. In the control period no participants receive intervention and sequential random crossover to the intervention cannot be reversed (166).

An important advantage of the stepped wedge design is that families only need to consent to participate in a research study and not to be randomized. In our experience this makes a big difference not only to the families, but also the front personnel who are recruiting the families. With a longer recruitment period and higher expected acceptance rates, the stepped wedge design will

INFANT HEALTH

[figure not shown]
result in a larger sample size and less frustration about recruitment among the CHNs who find it very hard to deliver standard care to families, when they have introduced an intervention, they believe is superior. Thus, we believe that the stepped wedge design is associated with the least dropout.

On a practical level, the 16 participating municipalities will be randomly distributed into three clusters (6+5+5), and clusters will be randomized to initiate intervention at three different time points, according to the stepped-wedge design (see Figure 1, flow diagram revised October 2022) (Detailed overview of the design, see Appendix 1).

Figure 1. CONSORT diagram

INFANT HEALTH

Randomization and screening (PUF) at child-age 9-10 months

According to the randomization of municipalities, all children assessed to have ≥ 3 problems will function as controls and receive care as usual from Step 0 until the municipalities initiate the intervention in Step 1- 3, respectively.

Recruitment of municipalities, children, and parents

INFANT HEALTH

[figure not shown]
All municipalities that have implemented the basic PUF-program are invited, and the leading CHNs from the becoming study municipalities are invited to join the study planning group as key stakeholders.

In the participating municipalities, the parents of children becoming 9-10 months in the study period are informed about the project by the CHNs, and via written folders and information on the study home page (<https://www.sdu.dk/da/sif>). At the scheduled home visit at child ages 9-10 months, the CHNs complete PUF-assessment and offer the parents feedback in accordance with the basic PUF-program and the existing routines. All parents of children who have been assessed to have three or more problems are offered extended service, in the control phase of the study this is delivered in accordance with the existing routines of the CHNs in the particular municipalities (care as usual), whereas the CHNs offer the VIPP-PUF intervention to parents in the intervention phase. The CHN informs all parents of infants full-filling the study criteria of inclusion about the details in the Infant Health project, and if parents are interested, they are invited for participation by e-post. Parents make their final agreement for participation by answering the web-based questionnaires at the study website.

Across the stage of recruitment, the CHNs assist parents in gaining information about the study, and if needed assistance in completing the questionnaires (e.g parent with cognitive difficulties).

Participating parents join a lottery with gift certificate of about 40 euro.

Figure 2. The Work Packages (WP) of the project

INFANT HEALTH

